### **Effect of covariates on the HR estimate (Cox Proportional Hazards model)**

As a sensitivity analysis, an unstratified Cox-proportional hazards modeling will be employed to assess the effect of covariates on the HR estimate for the primary analysis, i.e., the MODEL statement will include the treatment group variable and also the stratification factors (PD-L1 Status, smoking status and tumor location) as main effects. Hazard ratio with associated 95% CI will be based the profile likelihood approach.

This model will be done to ensure that any output from the Cox modeling is likely to be consistent with the results of the stratified log-rank test.

Moreover, another sensitivity analysis will be performed to evaluate the treatment effect, adjusted for pre-specified baseline prognostic factors. This analysis will be performed for the PD-L1 TC/IC high subgroup, low risk of EM subgroup, ctDNA TMB high ( $\geq 16$  mut/Mb) subgroup and all-comers. For this analysis, a stratified Cox model adjusted for the following covariates will be used. The covariates are:

- Sex at randomization (Male, Female)
- Age at randomization (<65,  $\geq 65 < 75$ ,  $\geq 75$  years of age)
- Race (Asian, non-Asian)
- WHO/ECOG performance status (0,  $\geq 1$ )
- Primary Tumor location/HPV (OPC/Positive, OPC/Negative, non-OPC/Any HPV)

- Extent of Disease (only locoregionally recurrent, metastatic with or without locoregional recurrence)

The Hazard ratio with two-sided 95% confidence interval will be based on profile likelihood approach.

The two models described above will include the effect regardless of whether the inclusion of effect significantly improves the fit of the model providing there is enough data to make them meaningful.

Interactions between treatment and the stratification factors will also be tested to rule out any qualitative interaction using the approach of [Gail and Simon 1985](#).

### **Assumptions of Proportionality**

For OS, the assumption of proportionality will be assessed. Proportional hazards will be checked first by examining plots of complementary log-log (event times) versus log (time) and, if these raise concerns, by fitting a time-dependent covariate to assess the extent to which this represents random variation. If a lack of proportionality is evident, the variation in treatment effect will be described by presenting piecewise HR calculated over distinct time periods. In such circumstances, the HR can still be meaningfully interpreted as an average HR over time unless there is extensive crossing of the survival curves. If lack of proportionality is found, this may be a result of treatment-by-covariate interactions, which may be investigated.

The Grambsch-Therneau non-proportionality test may also be used to check violation of the proportional hazards assumption ([Grambsch and Therneau 1994](#)). If a lack of proportionality is evident, the stratified max-combo test ([Karrison 2016](#)) will be conducted as a sensitivity analysis for OS to test for treatment differences in the case of non-proportional hazards. The max-combo test is based on an adaptive procedure optimizing test statistics among the log-rank test ( $FH^{0,0}$ ) and the Fleming-Harrington (FH) test ( $FH^{0,1}$ ;  $FH^{1,0}$ ) with alpha correction, and it is recommended by the Cross-Pharma Non-Proportional Hazards Working Group in the presence of non-proportional hazards ([Lin et al 2020](#)). This analysis will be produced by the Sponsor.

#### **4.2.2 Subgroup analysis OS**

Subgroup analyses will be conducted comparing OS between MEDI4736 + tremelimumab combination therapy versus SoC, MEDI4736 monotherapy versus SoC and MEDI4736+ tremelimumab combination therapy versus MEDI4736 monotherapy (in the PD-L1 TC/IC high subgroup, low risk of EM subgroup, ctDNA TMB high ( $\geq 16$  mut/Mb) subgroup and all-comers) for the following subgroups (but not limited to):

- Sex (male, female)
- Age at randomization (<65,  $\geq 65 < 75$ ,  $\geq 75$  years of age)

- PD-L1 TC status for stratification (positive, negative)
- CCI
- PD-L1 TC/IC status (TC $\geq$ 50 or IC $\geq$ 25 (High), TC $<$ 50 and IC $<$ 25(Low))
- ctDNA TMB (high ( $\geq$ 16 mut/Mb), low ( $<$ 16 mut/Mb), unknown)
- Tumor location/HPV (OPC/Positive, OPC/Negative, non-OPC/Any HPV),
- Primary tumor site (Oral cavity, Oropharynx, Larynx, Hypopharynx)
- Smoking history ( $>$ 10,  $\leq$ 10 pack-years)
- Race (Asian, non-Asian)
- ECOG Performance status (0,1)
- Extent of Disease (only locoregionally recurrent, metastatic with or without locoregional recurrence)

For these subgroup analyses any patient with missing values will be excluded from that particular subgroup.

Treatment effect will be estimated by the HR together with its corresponding 95% CI using an unstratified Cox model with treatment as the only covariate. Hazard ratio with two-sided 95% confidence interval will be based on the profile likelihood approach

A forest plot will be presented for the subgroups showing the comparison of MEDI4736+ tremelimumab combination therapy versus SoC, MEDI4736 monotherapy versus SoC and MEDI4736+ tremelimumab combination therapy versus MEDI4736 monotherapy for the analysis populations described above.

The subgroup analyses for the stratification factors will be based on the values recorded on the eCRF as indicated above. Other baseline variables may also be assessed if there is clinical justification or if an imbalance is observed between the treatment arms. The purpose of the subgroup analyses is to assess the consistency of treatment effect across expected prognostic and/or predictive factors. Only the HR estimate along with 95% CI will be presented.

No adjustment to the significance level for testing of the subgroup and sensitivity analyses will be made since all these analyses will be considered supportive of the analysis of OS.

If there are too few events available for a meaningful analysis of a particular subgroup comparison (it is not considered appropriate to present analyses where there are less than 20 events within a subgroup category (i.e., when the events in the treatment comparison does not add up to 20) in a subgroup), the relationship between that subgroup and the primary endpoint (OS) will not be formally analyzed. In this case, only descriptive summaries will be provided.

### **4.2.3 Analysis of the secondary variable (PFS)**

The analysis of PFS will be based on the programmatically derived RECIST 1.1 using the site investigator assessments. The analysis will be performed using a stratified log-rank test stratified by PD-L1 status (positive versus negative), tumor location (OPC versus non-OPC, with a subsequent adjustment for HPV status in patients with OPC), and smoking history (>10 versus  $\leq 10$  pack-years) for generation of the p-value.

The stratification factors will be based on the values entered into IVRS at randomization even if it is subsequently discovered that these values were incorrect.

The effect of MEDI4736 monotherapy therapy versus SoC treatment in the relevant analysis populations (Table 12), will be estimated by the HR together with its corresponding 95% CI. The hazard ratio (HR) of PFS, along with its 95% confidence interval using the same strata information as above will be estimated using a stratified Cox proportional hazards model with treatment a as the only covariate (with ties= Efron and any stratification variables included in the strata statement) and the CI calculated using a profile likelihood approach

PFS analysis will also be performed to compare MEDI4736 + tremelimumab combination therapy versus SoC as well as to compare MEDI4736 + tremelimumab combination therapy versus MEDI4736 monotherapy for the analysis populations detailed in Table 12.

These analyses will be performed using the same methodology as for the primary objective described above.

Kaplan-Meier plots of PFS will be presented by treatment arm. Summaries of the number and percentage of patients experiencing a PFS event and the type of event (RECIST 1.1 or death) will be provided along with median PFS for each treatment.

#### **Sensitivity analyses for PFS variable:**

A sensitivity analysis of PFS using the BICR tumor data will be performed.

An sensitivity analysis of PFS using site investigator assessment based on RECIST 1.1 modified for confirmation of progression will be performed. The stratified log-rank test used for the secondary analysis of PFS will be repeated.

Furthermore, disagreements between the investigator and BICR assessment will also be summarised. Since the data cut-off for the last BICR is Jan 8th, 2018, this data cut-off will also be used for the investigator assessment in this table to allow for a fair comparison.

#### **Subgroup analysis for PFS**

Subgroup analyses will be conducted comparing PFS between MEDI4736  $\pm$  tremelimumab combination therapy versus SoC. This subgroup analysis will be performed using the same subgroups and methodology from the OS subgroup analyses described in Section [4.2.2](#).

#### **4.2.4 Objective response rate**

The ORR will be based on the programmatically derived RECIST 1.1 using site investigator tumor data. The ORR will be compared between MEDI4736 monotherapy versus SoC using logistic regression models adjusting for the same factors as the primary endpoint (PD-L1 status, tumor location, and smoking history). The results of the analysis will be presented in terms of an odds ratio together with its associated profile likelihood 95% CI (e.g. using the option 'LRCI' in SAS procedure GENMOD) and p-value (based on twice the change in log-likelihood resulting from the addition of a treatment factor to the model).

A similar analysis will be performed for the comparison between MEDI4736 + tremelimumab combination versus SoC and between MEDI4736 + tremelimumab combination versus MEDI4736 monotherapy in for the analysis populations detailed in Table 12.

Summaries will be produced that present the number and percentage of patients with a tumor response (CR/PR). Overall visit response data will be listed and summarized over time for all patients (i.e., the FAS).

#### **Subgroup analysis for ORR**

The analysis using logistic regression to compare ORR between MEDI4736 ± tremelimumab combination therapy versus SoC will also be presented by subgroup. This subgroup analysis will be performed using the same subgroups from the OS subgroup analysis described in Section 4.2.2.

##### **4.2.4.1 Best Objective Response (BoR)**

BoR based on site investigator data (RECIST 1.1), for each treatment arm, BoR will be summarized by n (%) for each category (CR, PR, SD, PD, and NE). No formal statistical analyses are planned for BoR.

#### **4.2.5 Duration of response**

Descriptive data will be provided for the DoR in responding patients (i.e. median duration of response and 95% CIs) by treatment arm, including the associated Kaplan-Meier curves (without any formal comparison of treatment arms or p-value attached). Swimmer plots will be produced. This depicts each patient's nature and duration of response as a separate bar (horizontally) over time, ordered from the longest time in study to the shortest time in study.

#### **4.2.6 Time to response**

The TTR, based upon the site investigator assessment of RECIST 1.1, will be summarised (i.e., number of patients [%] based upon the number of responders) by the scheduled assessment timepoint that the response was first observed. Additionally, descriptive summary statistics (i.e., minimum, maximum, median, Q1 and Q3) will also be presented.

As a sensitivity analysis, time to response will also be summarised based upon the site investigator tumor assessment data according to RECIST 1.1.

This analysis will be performed on all-comers and the PD-L1 TC/IC subgroup population

#### **4.2.7 Proportion of patients alive and progression free at 6 and 12 months (APF12)**

The APF6 and APF12 will be summarized (using the Kaplan-Meier estimate) and presented by treatment arm.

#### **4.2.8 Time from randomization to PFS2**

PFS2 will be analyzed using a stratified log-rank tests, using the same methodology as described for the PFS endpoint. The effect of MEDI4736 + tremelimumab combination therapy versus SoC and the effect of MEDI4736 monotherapy versus SoC will be estimated by the HR together with its corresponding CI and p-value. Kaplan-Meier plots will be presented by treatment arm. Summaries of the number and percentage of patients who have an event as well as who were censored will be provided along with the medians for each treatment.

#### **4.2.9 Time from randomization to first and second subsequent therapy or death**

For supportive purposes, the time to the start of first and the second subsequent therapy or death will be analyzed using the same methodology and model as that used for the analysis of PFS. The HR for the treatment effect together with its 95% CI will be presented. In addition, a Kaplan-Meier plot of the time to the start of first and the second subsequent therapy will be presented by treatment arm, and the time between progression and start of first and the second subsequent therapy will be assessed. This interval will be summarized per treatment arm, but no formal comparisons will be made. No multiplicity adjustment will be applied as this is viewed as a supportive endpoint.

In patients who received subsequent anticancer therapy, a summary table of first and the second subsequent anticancer therapies by treatment arm will be provided, as well as response to first and the second subsequent anticancer therapy by treatment arm (if available).

The number of patients prematurely censored will also be summarized.

#### **4.2.10 Analysis of OS12, OS18 & OS24**

OS12, OS18 and OS24 will be summarized (using the Kaplan-Meier estimate) and presented by treatment arm.

#### **4.2.11 Change in tumor size**

Tumor size will be presented graphically using waterfall plots, to present each subject's best percentage change in tumor size as a separate bar, with the bars ordered from the largest increase to the largest decrease. Reference lines at the +20% and -30% change in tumor size levels will be added to the plots, which correspond with the definitions of progression and 'partial' response respectively. Additional waterfall plots showing percentage change in tumor size at specific timepoints may be produced if it is felt that these are warranted to provide greater clarity.

Additionally, ‘spider’ plots will be produced. This depicts each patient’s percentage change in tumor size at each visit as a line over time.

The above outputs will be programmed for the site investigator data based upon RECIST 1.1 assessments.

#### **4.2.12 Patient reported outcome**

The PRO endpoints that have been identified as secondary are EORTC QLQ-C30 time to HRQoL deterioration for global health status, time to symptom deterioration for fatigue, time to symptom deterioration for functional deterioration for physical domain and QLQ-H&N35 time to symptom deterioration for these 2 symptoms; pain and swallowing. These are not part of the main multiple testing procedures and as supportive endpoints will need a Bonferroni adjustment to the significance level to aid interpretation. Therefore, these 5 endpoints will be tested at a 1.0% significance level and 99% CIs will be produced for the comparison of MEDI4736 versus SoC.

The other time to symptom deterioration endpoints will be tested at a 5% significance level and 95% CIs will be produced. Compliance rates summarizing questionnaire completion at each visit will be tabulated.

If missing data is substantial, multiple imputation approach and pattern-mixture model may be explored where appropriate.

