8.5.3 Patient-reported outcomes

The PRO endpoints that have been identified as secondary objectives are EORTC QLQ-C30 time to HRQoL deterioration for global health status, time to symptom deterioration for functional physical domain, time to symptom deterioration for fatigue, and QLQ-H&N35 time to symptom deterioration for these 2 symptoms; pain and swallowing. These are not part of the main MTP, and as supportive endpoints will need a Bonferroni

adjustment to the significance level to aid interpretation. Therefore, these 5 endpoints will be tested at a 1.0% significance level and 99% CIs will be produced.

The other time to symptom deterioration endpoints will be tested at a 5% significance level and 95% CIs will be produced.

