8.5.3.1 EORTC QLQ-C30

Time to symptom deterioration in the PD-L1 TC/IC high subgroup and all-comers will be analyzed for each of the 3 symptom scales (fatigue, pain, and nausea/vomiting). Time to HRQoL/function deterioration in all-comers will be analyzed for the 5 function scales (physical, role, emotional, cognitive, and social) and global health status/QoL. These analyses will be done using a stratified log-rank test (at the 5% significance level), using the same methodology as described for the primary PFS endpoint.

The effect of MEDI4736 monotherapy versus SoC will be estimated by the HR together with its corresponding CI and p-value, using an unstratified Cox model with treatment as the only covariate. Time to deterioration will be presented using a Kaplan-Meier plot for each of the 3 symptom scales (fatigue, pain, and nausea/vomiting), 5 functional scales (physical, role, emotional, cognitive, and social), and global health status/QoL by treatment arm. Summaries of the number and percentage of patients who have an event as well as who were censored will be provided along with the medians for each treatment.

A summary of the symptom improvement rate for each of the 3 symptom scales (fatigue, pain and nausea/vomiting) will be produced. Similarly, a summary of QoL/function improvement rate for each of the 5 function scales (physical, role, emotional, cognitive, and social) and global health status/QoL will be produced. Symptom improvement rate and HRQoL/function improvement rate will be analyzed by comparing between treatment arms using a logistic regression model as described for the analysis of ORR.

Summaries of absolute and change from baseline values for each of the 3 symptom scales/items (fatigue, pain, and nausea/vomiting), 5 individual symptom items (dyspnea, insomnia, appetite loss, constipation, and diarrhea), 5 functional scales (physical, role, emotional, cognitive, and social) and the global health status\QoL score, and each functional domain will be reported by visit for each treatment arm. Graphical presentations may also be produced as appropriate.

Analysis of HRQoL or symptom will also be carried out by comparing mean change from baseline in the global health status/QoL, functions (physical, role, cognitive, social and emotional) scores (from the EORTC QLQ-C30 questionnaire).

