8.5.3.2 EORTC QLQ-H&N35

Time to symptom deterioration in the PD-L1 TC/IC high subgroup and all-comers for each of the 4 symptom scales/items in the QLQ-H&N35 (pain, swallowing, senses and speech) will be compared between treatment arms using a stratified log-rank test (at the 5% significance level) as described for the primary analysis of OS.

The effect of MEDI4736 monotherapy versus SoC will be estimated by the HR together with its corresponding CI and p-value, using an unstratified Cox model with treatment as the only covariate.

For each of the above 4 symptom scales/items in the QLQ-H&N35, time to deterioration in symptoms will be presented using a Kaplan-Meier plot. Summaries of the number and percentage of patients experiencing a clinically meaningful deterioration or death, and the median time to deterioration, will also be provided for each treatment group.

A summary of the symptom improvement rate for each of the 4 symptom scales/items mentioned above will be produced. The symptom improvement rate will be compared between treatment groups using a logistic regression model as described for ORR.

Summaries of absolute and change from baseline values for each of the 7 symptom scales/items (pain, swallowing, senses, speech, social eating, social contact and sexuality) and 11 single-item measures (teeth, problems with mouth opening, dry mouth, sticky saliva, coughing, feeling ill, use of analgesics, use of nutritional supplements, use of a feeding tube, weight gain, and weight loss) will be reported by visit for each treatment group. Graphical presentations may also be produced as appropriate.

The assessment of symptoms comparing mean change from baseline using the MMRM as described for EORTC QLQ-C30 will be repeated for pain, swallowing, senses, and speech of the EORTC QLQ-H&N35. All assumptions and outputs as described for the EORTC QLQ-C30 are applicable and the same approach from EORTC QLQ-C30 will be applied.

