Baseline will be the last assessment of the variable under consideration prior to the intake of the first dose of IP, except for efficacy variables. For efficacy variables, baseline is defined as the last visit prior to randomization. For PRO variables, baseline will be defined as the latest evaluable assessment on or prior to date of first dose.

Outcomes variables will be summarized and analyzed based on the analysis populations detailed in Tables 6 and 12. All outputs will be summarized by treatment arm.

In terms of retreatment, individual efficacy response data from the re-treatment phase will only be listed, however data from retreatment will be included in all PRO analyses. Any

derivations relative to baseline (e.g., day, RECIST derivations) in the retreatment period will be relative to the baseline scan prior to the retreatment period.

Note that the AEs, SAEs and AESI/AEPI events will be reported regardless of whether the event occurred during re-treatment period or not. Additionally, if there are sufficient numbers of retreated patients to warrant separate summaries following combinations of summaries would also be produced:

The period for assessing safety data from the retreatment phase will start at the date of first dose in the retreatment phase

- A small set of headline summaries of AE data from the retreatment phase only.

Table 12 details which efficacy endpoints are to be analyzed, together with pre-planned sensitivity analyses indicating which analysis is regarded as primary for that endpoint. Formal statistical analysis will be done for only OS endpoint. Nominal p-values will be provided for all other endpoint and sensitivity analyses. No adjustments for multiple testing of endpoints or subgroups will be made.

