##### **4.2.12.1 EORTC QLQ-C30**

Time to symptom deterioration will be analyzed for each of the 3 symptom scales (fatigue, pain, and nausea/vomiting). Time to HRQoL/function deterioration will be analyzed for the 5 function scales (physical, role, emotional, cognitive, and social) and global health status/QoL.

This will be achieved by comparing treatment arms using a stratified log-rank test as described for the PFS and OS analysis. The effect of MEDI4736 monotherapy versus SoC and MEDI4736 + tremelimumab combination therapy versus SoC treatment will be estimated by the HR together with its corresponding 95% CI using stratified Cox model with the same approach as described for PFS and OS analysis.

Time to deterioration will be presented using a Kaplan-Meier plot for each of the 3 symptom scales (fatigue, pain, and nausea/vomiting), 5 functional scales (physical, role, emotional, cognitive, and social), and global health status/QoL.

A summary of the symptom improvement rate for each of the 3 symptom scales (fatigue, pain, and nausea/vomiting) items will be produced. Similarly, a summary of HRQoL/function improvement rate for each of the 5 function scales (physical, role, emotional, cognitive, and social) and global health status/QoL will be produced. Symptom improvement rate for each of the 3 symptom scales (fatigue, pain, and nausea/vomiting) and HRQoL/function

improvement rate for each of the 5 function scales (physical, role, emotional, cognitive, and social) and global health status/QoL will be analyzed by comparing between treatment arms using a logistic regression model as described for the analysis of ORR.

Summaries of absolute and change from baseline values for each of the 3 symptom scales/items (fatigue, pain, and nausea/vomiting), 5 individual symptom items (dyspnea, insomnia, appetite loss, constipation, and diarrhea), 5 functional scales (physical, role, emotional, cognitive, and social), and the global health status\QoL score will be reported by visit for each treatment arm provided at least one treatment arm has 20 or more subjects with data at a given visit. Graphical presentations may also be produced as appropriate.

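### Five supportive PRO endpoints are assigned a 1.0% level and 99% CIs, but the Protocol sub-sections test the same scales at 5%, the SAP sub-sections give them 95% CIs, and SAP 4.1 says no adjustment is made

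*SAP*

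**What the plan says.** Both parent sections set the same rule. Protocol 8.5.3 names five PRO endpoints tied to secondary objectives, calls them supportive and outside the main testing procedure, and asks for a Bonferroni adjustment: "Therefore, these 5 endpoints will be tested at a 1.0% significance level and 99% CIs will be produced". It then adds: "The other time to symptom deterioration endpoints will be tested at a 5% significance level and 95% CIs will be produced". SAP 4.2.12 repeats both parts and limits the stricter rule to one comparison: "these 5 endpoints will be tested at a 1.0% significance level and 99% CIs will be produced for the comparison of MEDI4736 versus SoC".

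The sections beneath them, and the SAP's general principles, read differently:

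- Protocol 8.5.3.1 covers fatigue, the physical function scale and global health among other QLQ-C30 scales, and says: "These analyses will be done using a stratified log-rank test (at the 5% significance level").
- Protocol 8.5.3.2 covers QLQ-H&N35 pain and swallowing, with senses and speech, "using a stratified log-rank test (at the 5% significance level) as described for the primary analysis of OS".
- SAP 4.2.12.1 and 4.2.12.2 cover the same scales. In both, the effect of monotherapy versus SoC, and of the combination versus SoC, "will be estimated by the HR together with its corresponding 95% CI using stratified Cox model".
- SAP 4.1 confines formal analysis to OS, gives nominal p-values for every other endpoint, and states: "No adjustments for multiple testing of endpoints or subgroups will be made". That text introduces SAP Table 12, which includes PRO time to deterioration.

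**The concern.** The parent sections deliberately treat five endpoints more strictly than the rest. The sections that describe the analyses name those same endpoints and give the ordinary level or the ordinary CI, with no exception. In the Protocol the conflict is on the test level; its sub-sections state no CI percentage. In the SAP it is mainly on CI width, because 4.2.12.1 and 4.2.12.2 set no significance level of their own.

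In practice, a p-value between 0.01 and 0.05 counts as significant under Protocol 8.5.3.1 or 8.5.3.2 and not under Protocol 8.5.3 or SAP 4.2.12. A programmer following SAP 4.2.12.1 would produce a 95% interval, which could exclude 1 beside a test that fails at 1.0%. The trial is open-label and these PROs are named secondary outcomes, so the threshold for reading them should be fixed in one form before results are seen.

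**Working it through.** **1. The plan's own figure.** There are five endpoints, each at 1.0% (Protocol 8.5.3, SAP 4.2.12). Bonferroni gives 0.05/5 = 0.010, and the matching interval is 1 − 0.01 = 99%. The figure reproduces. The overall 5% for this family is inferred from 5 × 1.0%; neither section states it.

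**2. The passages side by side.**

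| Endpoint | Protocol 8.5.3 and SAP 4.2.12 | Protocol sub-section, test level | SAP sub-section, CI |
|---|---|---|---|
| Global health, physical function, fatigue (QLQ-C30) | 1.0%, 99% CI | 5% (8.5.3.1) | 95% (4.2.12.1) |
| Pain, swallowing (QLQ-H&N35) | 1.0%, 99% CI | 5% (8.5.3.2) | 95% (4.2.12.2) |
| Other time-to-deterioration scales | 5%, 95% CI | 5% | 95% |

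Only the last row agrees throughout. For combination versus SoC, the 95% CI does not conflict with SAP 4.2.12, which limits its rule to MEDI4736 versus SoC. Protocol 8.5.3 names no comparison, so its scope is open.

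**3. False positives across the five tests, one comparison in one population.**

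- At 1.0% each: bound 5 × 0.01 = 0.05; if independent, 1 − 0.99^5 = 0.0490.
- At 5% each: bound 5 × 0.05 = 0.25; if independent, 1 − 0.95^5 = 0.2262.

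**4. Chance that one endpoint falls where the two levels disagree.** This is P(1.960 < |Z| < 2.576) for a normal test statistic, and it needs no event count.

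- No true effect: 0.05 − 0.01 = 0.04.
- Largest value under any true effect: 0.242, reached when the mean of Z is (1.960 + 2.576)/2 = 2.268.

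**5. CI width.** On the log-HR scale the ratio of 99% to 95% is 2.576/1.960 = 1.31.

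**The case against.** The strongest reply is that the intended rule can be seen. The parent sections single out five endpoints and send the others to 5% and 95%. The sub-sections describe the method for nine QLQ-C30 and four QLQ-H&N35 scales together. Protocol 8.5 and SAP 4.1 make 95% CIs the default unless something else is stated, and the parent sections do state something else. This stands as evidence of intent. It does not reconcile the text: the sub-sections name the five scales themselves, and the 95% in SAP 4.2.12.1 and 4.2.12.2 is explicit, not a default.

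A second reply is that a nominal p-value can be reported and still be read against 1.0% as an aid to interpretation. That answers the nominal p-value sentence in SAP 4.1. It does not answer the sentence after it, which rules out adjustment for multiple endpoints while SAP 4.2.12 requires one.

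Three stronger readings are tempting, and the documents do not support them:

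- *The trial's type I error is compromised.* Both documents place these endpoints outside the testing procedure, and SAP Section 4 defines success by the OS hypothesis.
- *The PRO family will be tested with a 25% error bound.* That figure applies only if the 5% in the Protocol sub-sections governs. The SAP sub-sections set no competing test level.
- *The Bonferroni divisor is wrong because PROs are analysed in both all-comers and the PD-L1 TC/IC high subgroup.* The PD-L1 TC/IC set is by definition a subset of the FAS, and neither document promises control across populations. Not naming one population is a missing detail and contradicts nothing.

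**Conclusion.** The inconsistency is real as written. The Protocol gives two test levels for five named endpoints, the SAP gives two CI widths for the same endpoints in monotherapy versus SoC, and SAP 4.1 denies an adjustment that SAP 4.2.12 requires. The 1.0%/99% rule is evidently the one meant, and its arithmetic is correct.

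The size is modest. The difference between the readings is a false-positive bound of 5% against 25% over five tests (4.9% against 22.6% if the tests were independent, which correlated PRO scales will not be exactly). For a single endpoint, the chance that the level decides the reading is 4% with no effect and at most about 24% under any effect, assuming a normal test statistic. The p-values themselves are the same under either level; what changes is how they are read and which interval is printed. The OS analysis and its hierarchy are untouched. The wording should be corrected, but no conclusion about the primary objective depends on it.

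**What to change.** Keep the sponsor's own Bonferroni rule and make the other places agree with it:

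1. In Protocol 8.5.3.1 and 8.5.3.2, except the five endpoints, for MEDI4736 monotherapy versus SoC, from the stated 5% level and refer to Protocol 8.5.3.
2. In SAP 4.2.12.1 and 4.2.12.2, state 99% CIs for these endpoints in that comparison, leaving 95% for the remaining scales and for combination versus SoC.
3. In SAP 4.1, add an exception referring to Section 4.2.12 to both the nominal p-value sentence and the sentence ruling out adjustment.
4. In Protocol 8.5.3, name MEDI4736 monotherapy versus SoC as the comparison to which the 1.0% level applies, to match SAP 4.2.12. Combination versus SoC on these endpoints is then nominal.

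This is wording only, with no new data and no additional analysis. The price is that intervals for five supportive endpoints are 1.31 times wider on the log-HR scale than at 95%, which the parent sections already accept.
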